### • Month 3 from first administration of trial drug

Every effort will be made to conduct this review appointment by clinic visit, but in exceptional circumstances it could be done by telephone interview. During this 3-month review appointment: (a) Actively seek whether muscle symptoms have occurred: **if** NEW and SIGNIFICANT muscle pain or weakness have occurred then measure contemporary ALT\*/AST and CK; (b) Record any serious adverse event (including any possible cardiovascular event - please see Appendix 5 for definition of cardiovascular event and Section 9 for detailed definitions of SAEs) and record length of any in-patient stay, whether for elective/planned procedures or not; (c) Review ALT/AST result: if ALT/AST available from within the last 6

weeks while patient was taking study treatment, other treatment was stable, and no new and significant muscle symptoms have been reported, then this value may be accepted and recorded in CRF with the date measurement was done; if ALT/AST not available within the last 6 weeks then request test and review result before advising patient whether they should / should not continue on study medication. (d) Record current relevant medication.

### • 6- monthly from randomization

Follow-up may be conducted either by attendance at clinic or by telephone interview, but every effort will be made to have one clinic review appointment per year. During these 6-monthly reviews act as above (3-month review) but also record HAQ and EQ5D annually since randomisation.

### In the presence of new and significant muscle symptoms:

(a) if CK>10xULN, then stop trial medication - not to be restarted.

(b) if ALT/AST<2xULNand CK<3xULN, trial medication can be continued with clinical follow-up. Further measurements of ALT/AST and CK can be requested if thought to be necessary by managing rheumatologist.

(c) if ALT/AST >2xULN and/or CK between 3-10xULN retest in 1-2 weeks: (c1) if normalisation has occurred to ALT/AST<2xULN and CK<3xULN then act as per option (b) above; (c2) if CK>10xULN stop trial medication; (c3) if ALT/AST>2xULN and CK again between 3-10xULN retest in 1 week: if elevation persists then stop trial medication.

### In the absence of any new and significant muscle symptoms:

In general, if abnormalities of LFTs with atorvastatin are to occur, they are more likely to occur within the first 3-6 months of treatment. After that, any DMARD or non-steroidal therapy (or other medications) would be a more likely cause of LFT abnormalities and the managing rheumatologists should consider stopping these drugs prior to stopping the trial medication. Attribution of LFT abnormalities to the trial medication or anti-rheumatic drug is left to the managing rheumatologist, but the TRACE RA team, including the Chief and Lead Investigators or delegated person could advise, if necessary.

**If LFT abnormalities are thought to be attributable to anti-rheumatic medication rather than trial drug:** then follow usual rheumatology practice guidelines (e.g. BSR monitoring guidelines).

### If LFT abnormalities are thought to be attributable to trial drug rather than other reasons:

(a) If ALT/AST within normal range or <2xULN, then continue trial medication and arrange next follow-up.

(b) If ALT/AST between 2-3xULN then continue trial medication and retest in 1 week. (b1) if normalisation to <2xULN has occurred, then act as per option (a) above. (b2) if ALT/AST persists at between 2-3xULN or more, then temporarily stop trial medication and act as per option (c) below.

(c) If ALT/AST>3xULN continue trial medication and retest one week later: (c1) if ALT/AST has recovered to <2xULN then continue trial medication and act as per options (a) above; (c2) if ALT/AST between 2-3xULN then retest in 1 week and if ALT/AST persists at between 2-3xULN or more, temporarily stop trial medication and act as per option (c3); (c3) if ALT/AST elevation persists at >3xULN then temporarily stop trial medication and retest in 3 weeks: (c3i) if normalisation has occurred, then act as per options (a) or (b), whichever applies; (c3ii) if abnormality persists at >3xULN then stop trial medication – not to be restarted.

\*If ALT and AST are both available in a local hospital then ALT is to be preferred for liver monitoring since it is more liver specific than AST.

### Follow-up visits for TRACE RA DAS participants

- Month 6 from first administration of trial drug (TRACE RA DAS sub-study only)
   Patient Global Assessment (VAS)
   Nurse Global Assessment (VAS)
   28 tender and swollen joint count
   ESR and/or CRP
   → 4 x 2.5mls blood sample (for RNA analysis)
  - $\rightarrow$  2 x 10mls plasma blood sample

- $\rightarrow$  2 x 10mls serum (clotted) blood sample
- $\rightarrow$  1 x 4.5mls plasma (citrate) blood sample
- → Month 12 from first drug administration of trial drug (TRACE RA DAS sub-study only)
   Patient Global Assessment (VAS)
   Nurse Global Assessment (VAS)
   28 tender and swollen joint counts
   ESR and/or CRP
- Month 24 from first administration of trial drug (TRACE RA DAS sub-study only)
   Patient Global Assessment (VAS)
   Nurse Global Assessment (VAS)
   28 tender and swollen joint counts
   ESR and/or CRP

Patients in the TRACE RA DAS sub-study have a mandatory visit at 6 months at which the components of the DAS28 score are checked. Consultants are asked not to change the DMARD therapy of patients enrolled in the disease activity sub-study for the first 6 months of the clinical trial.

Additional visits to the rheumatology clinic and changes in medication will be decided based on clinical need. Patients will be given the telephone number of their consultant or Rheumatology department/helpline in case they have any concerns whilst enrolled on the trial.

Patients will continue the intervention for the entire period of their participation in the trial, unless the trial steering committee decides to discontinue the study for any reason. Any patients who discontinue the intervention will remain under follow up.

### 6.3 Procedure for unblinding

Each hospital pharmacy has a nominated person who can break the randomisation code for an individual patient if required in a medical or other emergency. The code (scratch card) for each individual patient is kept securely in the pharmacy. The local and main co-ordinating centre is informed each time the code is broken and is given the reason for the unblinding.

### 6.4 End of trial

The trial is currently planned to continue recruiting until March 2014 with the last follow-up appointment being in March 2016, or until a sufficient number of events has accrued to provide statistical power (currently calculated to be around 370 confirmed primary events) whichever is the earlier. All patients will be followed-up (by phone or attendance) 6-monthly until the trial has been completed and will stop their medication on the day of their final assessment. All events which occur prior to this final assessment will be included in the analysis whether or not the patient has continued to take the trial medication. Because of the 'intention-to-treat' (ITT) analysis, it is essential to follow all patients (including those that have reached a trial endpoint) up to this 'final assessment' date.

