### **10. STATISTICAL CONSIDERATIONS**

### 10.1 Sample size

The aim of the trial is to detect (with 80% power at the 5% significance level) a 32% relative risk reduction (RRR) in the primary endpoint attributable to treatment with atorvastatin and anticipating an average of 25% non-compliance. If the true effect of taking the treatment is a 32% RRR but only 75% of patients are compliant, then the effect seen in this trial should be about 24% (ie, 75% of 32%). The required number of first events (i.e. patients with events) to be able to detect such a reduction with 80% power at the 5% significance level is 434 (Appendix 8). The estimated average blinded event rate in all patients is expected to be 1.6-1.8% per annum. A maximum of around 27000 patient-years of follow-up is required for these event rates to produce the required number of first events (Appendix 8). Based on recruitment rates achieved between August 2007 and November 2010 and using a logarithmic decay model to reflect the decline in recruitment with time, it is estimated that 5342 patients recruited by March 2014 would provide between 27000 and 28000 patient-years of follow-up. If the blinded event rate is somewhat less than expected then the trial will continue (if necessary) until the required number of events has been accrued and all the available follow-up data will be used in the analysis.

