### 10.4 Planned analyses

All patients randomised will be included in the analysis, irrespective of whether the study drug is continued (ITT analysis). Cox regression models will be developed for time to occurrence of a first cardiovascular event or serious adverse event using treatment allocation as the independent variable.

The models will be adjusted for factors used in the stratification (centre) and for any baseline imbalances. However, the trial is of sufficient size to expect that most potential confounders (e.g. smoking, aspirin, NSAID/Coxib, corticosteroid, anti-TNF usage etc) are likely to be balanced between the groups. Treatment differences will be expressed as hazard ratios with 95% confidence intervals. Two-sided p values of  $\leq$ 0.05 will be considered significant.

Kaplan-Meier Product Limit (PL) estimates of the survival curves with 95% confidence intervals will be calculated.

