### **APPENDIX 8: POWER CALCULATION AND OTHER STATISTICAL CONSIDERATIONS**

#### Table 1

Total number of patients with events and total number of events required for Cox regression (80% power at 5% significance level)

Reduction in Annual Event Rate

(after adjustment for non-compliance)	Number of patients with events	Number of events*
20%	631	671
21%	565	597
22%	509	534
23%	460	481
24%	417	434
25%	379	393
26%	346	358
27%	317	327
28%	291	299

\*assuming independence of events

#### Table 2

Expected total number of events for various combinations of annual event rate and patient-years of follow-up

	Patient-Years Follow-up						
Annual event rate*		1.3%	1.4%	1.5%	1.6%	1.7%	1.8%
	25000	325	350	375	400	425	450
	26000	338	364	390	416	442	468
	27000	351	378	405	432	459	486
	28000	364	392	420	448	476	504

\*overall event rate in the two groups combined

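### Section 6.4 closes the trial at about 370 events or March 2016, whichever comes first; Section 10.1 and Appendix 8 need 417 patients with events for 80% power and promise to continue

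*Protocol*

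**What the plan says.** - **Section 6.4, End of trial.** Follow-up ends in March 2016 or when there are enough events for statistical power, given as "currently calculated to be around 370 confirmed primary events) whichever is the earlier". All events before each patient's final assessment enter the analysis.
- **Section 10.1, Sample size.** The aim is to detect, "with 80% power at the 5% significance level) a 32% relative risk reduction (RRR) in the primary endpoint", "anticipating an average of 25% non-compliance". The effect seen in the trial "should be about 24% (ie, 75% of 32"%). The number of first events, which the section equates with patients with events, needed "to be able to detect such a reduction with 80% power at the 5% significance level is 434 (Appendix 8"). If the blinded event rate is lower than expected, "then the trial will continue (if necessary) until the required number of events has been accrued".
- **Appendix 8, Table 1.** Headed "Total number of patients with events and total number of events required for Cox regression", it has two columns. The 24% row reads 417 patients with events and 434 events. Neither column contains 370.
- **Appendix 8, Table 2.** It gives expected total events by annual rate and patient-years. At 27,000 patient-years these are 432 to 486 for 1.6-1.8% and 351 to 405 for 1.3-1.5%.
- **Section 10.7.** Interim analyses fall at 25%, 50% and 75% of the expected total.

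**The concern.** Three figures (370, 417 and 434) are offered as the event count for the same power, and two closing rules exclude each other. Section 6.4 takes the earlier of a date and a count. Section 10.1 says follow-up is extended when events are slow. If accrual goes to plan, the 370 limit stops the trial before the planned follow-up is complete. If accrual is slow, Section 6.4 closes on the date while Section 10.1 says to carry on. The stopping point of the primary analysis is therefore not fixed, and Section 6.4 followed literally yields less than the stated power.

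**Working it through.** **Inputs.** Two-sided 5% (Section 10.4: "Two-sided p values of" 0.05 or less); 80% power; reduction 0.75 × 32% = 24%, so HR = 0.76 and ln(0.76) = -0.2744. Allocation is taken as 1:1. The protocol states no ratio, but Table 1 reproduces on that basis.

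**1. Reproduce Appendix 8, Table 1.** Schoenfeld: D = 4(1.960 + 0.842)² / (ln HR)² = 4 × 7.849 / 0.0753 = 416.9, the 417 in the patients column. The other rows, 20% to 28%, agree within one event. The events column follows from the independence assumption in the table's footnote with N = 5,342 patients (Section 10.1): first events = N(1 - exp(-E/N)). For E = 434, 5,342 × (1 - exp(-0.0812)) = 416.8. So 417 and 434 are one requirement in two units. The Cox analysis of time to first event needs 417; Section 10.1 attaches 434 to the wrong unit.

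**2. Can 370 be the same calculation?** For HR 0.76 and 80% power, Freedman's formula gives 423. One-sided 5% gives 329 (Schoenfeld) or 333 (Freedman). None gives 370. The figure fits 75% power at HR 0.76 (Schoenfeld 369), or 80% power at HR = exp(-2 × 2.802/√370) = 0.747, a 25.3% reduction.

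**3. Power at closure on 370, HR 0.76.** Power = Φ(√D/2 × 0.2744 - 1.960).

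| Meaning of 370 | First events D | Power |
|---|---|---|
| Patients with a first event | 370 | Φ(2.639 - 1.960) = 75.2% (Freedman 74.6%) |
| All events, formula in step 1 | 357 | 73.7% |
| All events, ratio 417/434 | 355 | about 73% |
| For comparison: Table 1 target | 417 | 80.0% |

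**4. Which limit binds at the planned rate?** 370/0.018 = 20,556 and 370/0.016 = 23,125 patient-years. Against 27,000 these are 23.9% and 14.4% short. This puts 370 and the rate in the same unit. If 370 means first events and the rate counts all events, 370 corresponds to -5,342 × ln(1 - 370/5,342) ≈ 383 events, or about 21,300 to 24,000 patient-years, still before 27,000. Either way the 370 limit closes the trial first.

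**5. What the date alone would cost.** Remove the 370 limit, close at 27,000 patient-years, and convert Table 2 totals to first events:

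| Annual rate | Total events (Table 2) | First events | Power |
|---|---|---|---|
| 1.3% | 351 | 340 | 71.5% |
| 1.4% | 378 | 365 | 74.6% |
| 1.5% | 405 | 390 | 77.3% |
| 1.6% | 432 | 415 | 79.8% |
| 1.7% | 459 | 440 | 82.1% |
| 1.8% | 486 | 465 | 84.1% |

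At the planned rates the date leaves power at about 80-84%. Below them it falls to about 72-77%, which is the case in which Section 10.1 promises to continue.

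**The case against.** The operative test in Section 6.4 is that events suffice for power; 370 is only a parenthesis, marked as current and approximate. Section 4 likewise ties recruitment to achieving the power in Section 10. That is fair, but Section 10.1 is equally current, and an approximation does not cover a gap of 47 (to 417) or 64 (to 434).

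The 75% is also somewhat pessimistic, because events keep counting until each patient's final assessment. As an illustration, assume about 4,950 event-free patients and an average close-out of three months: 4,950 × 0.25 × 0.016 to 0.018 adds about 20 to 22 events and brings power to about 77-78%. This stands as a reduction of the loss, not a removal of it.

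A reader might infer more than the protocol supports in three respects.

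- **That March 2016 by itself forfeits 80% power.** At the planned 1.6-1.8% and 27,000 patient-years it does not (step 5).
- **That 434 first events are needed.** Table 1 shows that 417 are; measuring the gap from 434 overstates it.
- **That the interim analyses are compromised.** Their total is ambiguous, but the first look moves only between about 93 events (25% of 370) and 109 (25% of 434), and Section 10.7 sets no formal boundary that depends on it.

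**Conclusion.** The contradiction is in the operative text and holds. Closing as Section 6.4 states gives about 75% power for the planned 24% reduction if 370 counts first events, and about 73-74% if it counts all events, against a stated 80%; close-out events recover part of the gap. At the planned event rate the 370 limit, not the date, causes the loss. The date matters only if the event rate or patient-years fall below plan, and there it conflicts directly with the promise in Section 10.1. The labelling of 434 as first events is a separate error and must be corrected with the rest. The figures rest on 1:1 allocation, proportional hazards at HR 0.76, and the protocol's own independence assumption for converting events to patients with events.

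**What to change.** 1. **Section 6.4:** replace 370 with 417 patients with a first confirmed primary event.
2. **Section 10.1:** replace 434 first events with 417 patients with events (434 events in all), so that target and counting unit agree across Sections 6.4 and 10.1 and Appendix 8.
3. **One closing rule.** Either (a) delete the earlier-of clause in Section 6.4, so that March 2016 is an expected date and the event target governs; or (b) if March 2016 is a hard limit, delete the sentence in Section 10.1 that promises to continue, remove the 370 limit, and state that 80% power holds only if about 417 first events accrue by then. At 27,000 patient-years that means about 80-84% power at 1.6-1.8% per year and about 72-77% at 1.3-1.5%.
4. **Section 10.7:** refer the interim fractions to the same total. This is a minor consequential edit.

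The cost is protocol wording. Under (a), 434 total events need 434/0.018 = 24,111 to 434/0.016 = 27,125 patient-years, within the 27,000-28,000 that Section 10.1 forecasts; slower accrual means the longer follow-up that Section 10.1 already accepts. Under (b), the cost is a power statement that depends on the event rate.

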### 7. DISCONTINUATION OF STUDY MEDICATION

Patients who experience a cardiovascular event will stop their study medication and take statin prescribed by their managing doctor. They will continue to be followed-up. Patients who, during the course of the trial, develop other indications for statin therapy (e.g. diabetes) can continue on the trial medication AND be prescribed unblinded statin, preferably atorvastatin up to a maximum dose of 40mg daily, or an alternative statin up to a maximum dose equivalent to atorvastatin 40mg daily. If a higher dose than this is required then the trial medication will be stopped and an unblinded statin prescribed. A record of any concomitant statin prescription will be made on the CRF. All patients will also continue to be followed-up in the trial.

If the trial is stopped early for safety reasons, all patients will stop the study medication. If it is stopped early due to efficacy of the statin arm, all patients will be offered the opportunity to continue/commence statin therapy. If the trial goes its full length, all patients will stop the trial medication and be managed according to their physician's preference pending full analysis and publication of the trial findings.

Patients are free to withdraw from the trial treatment at any point. This will have no implications on their future care.

Breaks in study medication: Should patients take a break in their study medication, they may recommence at any time provided /ALT/AST is within the screening limits within the last 6 weeks and other treatment has remained stable. ALT (or AST if ALT not available) should be checked 3 months after restarting study drug.

### 8. DRUG SUPPLIES AND LABELLING

Atorvastatin and the placebo atorvastatin are supplied free of charge by Pfizer UK Ltd.

### 8.1 Packaging and labelling of study medication

The drug is packaged in bottles and labelled by Catalent Pharma Solutions according to GMP standards. Bottles are labelled with a minimum of the following information:

- Unique drug number (number allocated to drug bottle)
- Packaging lot number
- Expiry date
- Number of tablets in bottle
- Dosage instructions
- Storage conditions

Bottling and labelling will be done in several runs spaced throughout the trial. All bottles contain extra tablets to allow for delays in patient visits.

### 8.2 Supply of study medication to centres

Catalent Pharma Solutions supplies the packaged drugs to the pharmacies of individual hospitals at regular intervals throughout the trial.

Patients are asked to return any unused medication to pharmacy which will be destroyed on site.

Patients are provided with a 6 monthly supply of the study medication. At the first visit they are advised that they must attend for a safety visit at 3 months and should only continue the medication beyond this point if advised to do so. Each time that the trial drug is dispensed, the pharmacy will be asked to affix the supplementary drug label to the prescription sheet so that a 'dispensing record' can be maintained.

# 9. PHARMACOVIGILANCE

### 9.1 Cardiovascular Outcomes and reporting of cardiovascular outcomes

Any cardiovascular event or endpoint experienced by a patient should be reported on the serious adverse events form that is provided in the site file, as these events will be classified as part of the endpoints of the trial. All information regarding a cardiovascular event should be faxed to the AR UK Epidemiology Unit at the University of Manchester on [name] within 24 hours of knowledge of the event. The local principal investigator or research nurse will be contacted by the trials unit if further information is required.

### 9.2 Serious Adverse Events (SAEs)

A Serious Adverse Event (SAE) is defined as any untoward medical occurrence that:

- results in death
- is life-threatening (i.e. with an immediate, not hypothetical, risk of death at the time of the event),
- requires hospitalisation or prolongs existing hospitalisation
- results in persistent or significant disability or incapacity,
- is a congenital anomaly or birth defect (i.e. the outcome of pregnancy involving the patient)
- any other important medical condition which, though not included in the above, may jeopardise the patient and may require medical or surgical intervention to prevent one of the outcomes listed (e.g. allergic bronchospasm requiring intensive emergency treatment, seizures or blood dyscrasias which do not result in hospitalisation, or development of drug dependency).

Medical judgement should be exercised in deciding whether an adverse event/reaction is serious in other situations. Hospitalisations include planned admissions for elective surgery.

All serious adverse events must be reported on the **serious adverse event form**. The SAE form should be faxed to the AR UK Epidemiology Unit at the University of Manchester on **[name] within 7 days** of knowledge of the event. The local principal investigator or research nurse will be contacted by the trials unit if further information is required.

### 9.3 Adverse Events

An adverse event is the development of an undesirable medical condition or the deterioration of a pre-existing medical condition following or during exposure to a pharmaceutical product, whether or not considered causally related to the product. An undesirable medical condition can be symptoms (eg, nausea, chest pain), signs (eg, tachycardia, enlarged liver) or the abnormal results of an investigation (eg, laboratory findings, electrocardiogram).

Adverse events (either serious or non-serious) which lead to discontinuation of study treatment should be routinely recorded on the CRF. Other adverse events need not be recorded in the CRF.

In addition, new significant muscle symptoms should be sought at each study visit and recorded. If present AND if ALT is greater than the upper limit of normal then a blood CK should be measured (see section 6.2.3)

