### TRACE RA tertiary endpoints

Total and cause-specific mortality (coronary, other vascular and non-vascular death separately) Hospitalisations for various other causes Statin safety-related outcomes (persistent elevation of ALT or AST; myopathy (defined as muscle symptoms plus CK>10 x upper limit normal) Differences in lipid levels during follow-up in a random sample Functional outcome assessed by HAQ and EQ5D

Allowance for multiple hypothesis testing in these analyses will be made using the "Bonferroni" correction.

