## APPENDIX 6: SAFETY OUTCOMES

Clinical laboratory safety parameters are shown below. Haematology and biochemistry will be performed at the local laboratories. All of the safety parameters are subject to routine regular monitoring for safety of the disease-modifying anti-rheumatic drugs (DMARDs). Such monitoring is required as part of routine clinical practice at intervals ranging between 2 weeks and 3 months for all but one DMARDs (the antimalarials). All patients will be questioned about muscle symptoms at each follow-up visit and if new and significant CK will be measured. Only serious adverse events will be recorded. Randomisation codes will be kept securely by participating pharmacists. If deemed necessary by the local investigator the randomisation code can be broken by contacting the local pharmacy.

Abnormalities of haematological and biochemical parameters in this population may be either due to DMARDs or the study drug. The decision of attribution will be left to the managing local investigator.

The study drug should be stopped if:

- Patient has new and significant muscle pains and CK>10xULN,Patient has new and significant muscle pains and ALT/AST >2xULN and CK between 3-10xULN and elevation persists upon retesting.
- Myopathy is diagnosed (muscle pain or weakness AND CK >10 times ULN)
- Elevation of CK to ≥5 times ULN, persisting on retesting 1 week later, should also lead to discontinuation of study medication.

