# APPENDIX 10: TRIAL EVALUATIONS SCHEMA \* DAS - TRACE RA DAS REQUIREMENTS

Trial Investigations		eline	Visit 2 Month 3 ALL	Visit 3 Month 6 DAS	Vis Mont	it 4 th 12 DAS	Visit 5 Month 18 ALL		sit 6 nth 24 DAS	Visit 7, 9, 11, 13, Month 30, 42, 54, 66,78 ALL	Visit 8, 10, 12, 14, 16 Month 48, 60 , 72, 84 ALL
		Dirio		DAG		Ditto			Drite		
Inclusion/Exclusion Criteria Assessments	✓	#									
Written Informed Consent	✓	#									
Height, Weight, BP	✓										
Medical History	1										
Concomitant Medication	✓		1		✓		1	1		✓	✓
ESR/CRP, RhF/anti-CCP, LFTs at baseline and LFTs at follow up visit	1				✓		~	1		1	1
Research DNA blood sample (BioBank)	✓										
Research serum and plasma (BioBank) *	1										
Research RNA sample (DAS)		#		#							
Research serum and plasma (DAS)		#		#							
Discussion of CVD risks	✓										
HAQ	✓			#	1			✓			4
EQ5D	✓			#	✓			1			✓
Lifestyle Questionnaire	1										
DAS 28 Tender & Swollen joint count	1			#		#			#		
Patient Global Assessment (VAS)	1			#		#			#		
Nurse Global Assessment (VAS)		#		#		#			#		
Check for Serious Adverse events &Cardiovascular events			~		1		✓	1		4	~
Drug compliance			1		*		4	1		1	1

Research serum and plasma sample for TRACE RA BioBank is not required if patient is enrolled in TRACE RA DAS ٠

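### Section 9.3 makes CK testing depend on a raised ALT, against section 6.2.3 and Appendix 6; and the CK algorithm has no final action for some persistent elevations, one of which Appendix 6 stops

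*Protocol*

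**What the plan says.** **When to measure CK.** Section 9.3 has sites look for new significant muscle symptoms at each visit and continues: "If present AND if ALT is greater than the upper limit of normal then a blood CK should be measured (see section 6.2.3". In section 6.2.3, the month 3 review has sites ask about muscle symptoms; if "NEW and SIGNIFICANT muscle pain or weakness have occurred then measure contemporary" ALT or AST, and CK. No ALT result has to come first. For the later visits, "During these 6-monthly reviews act as above (3-month review". Appendix 6 says: "All patients will be questioned about muscle symptoms at each follow-up visit and if new and significant CK will be measured".

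**What to do with the result.** Sections 6.2.3 and 11.2 carry the same algorithm for symptomatic patients:
- (a) CK above 10xULN: stop for good.
- (b) ALT/AST below 2xULN and CK below 3xULN: continue.
- (c) ALT/AST above 2xULN and/or CK 3-10xULN: retest in 1-2 weeks. Then (c1) continue if both have normalised to the limits in (b); (c2) stop if CK exceeds 10xULN; or "c3) if ALT/AST>2xULN and CK again between 3-10xULN retest in 1 week: if elevation persists then stop trial medication".

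Appendix 6 also stops at CK above 10xULN with symptoms, and for symptoms with ALT/AST above 2xULN and CK 3-10xULN that persists. It adds a further criterion: CK of 5xULN or more, "persisting on retesting 1 week later, should also lead to discontinuation of study medication". That criterion has no ALT condition.

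**The endpoint and the schedule.** Section 3.2 lists among the tertiary endpoints "myopathy (defined as muscle symptoms plus CK>10 x upper limit normal". The Appendix 10 schema has a row that includes "LFTs at baseline and LFTs at follow up visit" and no row for CK.

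**The concern.** Section 9.3 and the section it cites give different instructions for the same patient. Myopathy is defined by symptoms and CK, and section 11.2 names it as one of two recognised adverse effects monitored at every follow-up. If CK is taken only when ALT is also raised, a myopathy with normal ALT goes undetected, and the patient may stay on a drug that every section would stop once CK was known to exceed 10xULN.

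The second problem is in the stopping rules. A symptomatic patient with moderately raised, persistent CK and unremarkable ALT/AST is stopped under Appendix 6 but reaches no decision under 6.2.3 and 11.2. With up to 120 centres, different readings would make both the ascertainment of a safety endpoint and drug discontinuation uneven across sites.

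**Working it through.** No sample size, power or event count is involved, so the check sets the rules side by side and runs patients through them.

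**Step 1: CK trigger, given new and significant muscle symptoms.**

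| ALT | 9.3 | 6.2.3 (month 3 and every 6 months) | Appendix 6 |
|---|---|---|---|
| at or below ULN | CK not called for | CK | CK |
| above ULN | CK | CK | CK |

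The sections differ in the first row only. Step (b) of the algorithm confirms which rule was intended: it needs a CK result in a patient whose ALT/AST is below 2xULN, so the algorithm expects CK to be available when ALT is normal. A patient handled under 9.3 with normal ALT has no CK and cannot be placed in (b).

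No scheduled test fills the gap. Appendix 10 has no CK row, and the baseline bloods in 6.2.1 do not include CK. After randomisation, muscle symptoms are the only protocol-mandated route to a first CK.

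**Step 2: action, given symptoms and a result that persists on retest.**

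| CK | ALT/AST | 6.2.3 and 11.2 | Appendix 6 |
|---|---|---|---|
| above 10xULN | any | stop, (a) or (c2) | stop |
| 3-10xULN | above 2xULN | stop, (c3) | stop |
| 5-10xULN | below 2xULN | enters (c), no exit | stop if persisting at 1 week |
| 3-5xULN | below 2xULN | enters (c), no exit | no stop stated |
| below 3xULN | above 2xULN | enters (c), no exit | no stop stated |
| below 3xULN | below 2xULN | continue, (b) or (c1) | no stop stated |

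Take CK 7xULN with ALT/AST below 2xULN, unchanged on retest. The patient enters (c) because its entry condition is and/or. On retest (c1) fails because CK is not below 3xULN, (c2) fails because CK is not above 10xULN, and (c3) fails because ALT/AST is not above 2xULN. The algorithm ends without an action; Appendix 6 stops the drug. The fourth and fifth rows have the same structural gap, and there Appendix 6 does not fill it.

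**Step 3: timing where ALT/AST is also above 2xULN.** Under (c3) a stop comes after two retests, at (1 to 2 weeks) + 1 week = 2 to 3 weeks. Appendix 6 has two bullets that could apply to CK 5-10xULN. Its 3-10xULN bullet requires persistence on retesting but sets no number of retests, so it is compatible with (c3). Its 5xULN bullet gives one retest at 1 week. Only if the second bullet overrides the first is there a difference, of 2 - 1 = 1 week to 3 - 1 = 2 weeks.

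**Step 4: a minor slip in the liver algorithm.** In both 6.2.3 and 11.2, ALT step (b2) stops the drug temporarily and sends the reader to option (c), which opens by continuing it. The parallel step (c2) points to (c3), which is evidently where (b2) should point.

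**The case against.** The strongest defence is that 9.3 is not the operative procedure. It does not say that CK is to be taken only when ALT is raised, it forbids nothing, and it ends with a pointer to 6.2.3, where the right rule stands. 6.2.3 and Appendix 6 agree with each other, so a site that follows the pointer will take the CK. This limits the likely consequence. It does not remove the contradiction: the capitalised conjunction reads as a condition, and a cross-reference does not repair a sentence that disagrees with its target.

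On stopping, 11.2 opens by referring to Appendix 6 for safety outcomes, and the 5xULN criterion is worded there as an additional one. Read together, it can fill the gap for CK 5-10xULN with ALT/AST below 2xULN, and no section tells sites to continue the drug in that case. That is fair, so this part is best described as an algorithm without a final step, alongside a rule stated only in an appendix. The muscle algorithm in 6.2.3, which sites use at the visit, does not contain that rule.

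Three stronger readings are tempting and are not supported:
- **That following 6.2.3 or 11.2 keeps patients on the drug 1 to 2 weeks longer when ALT/AST is above 2xULN.** Both routes end in a stop, and the figure depends on which Appendix 6 bullet governs.
- **That CK could never be obtained except through symptoms.** Only the protocol-mandated route is meant. Appendix 6 states that its safety parameters are subject to routine DMARD monitoring, and its 5xULN rule is not tied to symptoms, so a CK may arise locally.
- **That myopathy will be missed.** It could be, at a site that reads 9.3 alone.

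**Conclusion.** The point holds in two parts. First, 9.3 contradicts 6.2.3 and Appendix 6 on the CK trigger for symptomatic patients with ALT at or below ULN; followed as written, it could miss myopathy as section 3.2 defines it. Second, for symptomatic patients with persistent CK 5-10xULN and ALT/AST not above 2xULN, 6.2.3 and 11.2 reach no decision while Appendix 6 stops the drug.

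The size is bounded in kind but not in number. The protocol gives no frequency for new muscle symptoms or for these CK and ALT combinations in this population, so the patients affected cannot be counted. The consequence also assumes that some sites act on 9.3, or on the algorithm, without reading the other sections. All sections agree on stopping above 10xULN once CK is known. The outcome concerned is a tertiary safety endpoint, and the primary analysis and the sample size are unaffected. It is worth correcting because it is a safety instruction and the correction is simple.

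**What to change.** 1. **Section 9.3:** delete the ALT condition. Suggested text: *If present, ALT/AST and CK should be measured (see section 6.2.3).*
2. **Sections 6.2.3 and 11.2:** add the existing Appendix 6 rule to the muscle-symptom algorithm: *If CK is 5xULN or more, retest at 1 week; if it is still 5xULN or more, stop trial medication, whatever the ALT/AST.* This also settles which Appendix 6 bullet governs at 5-10xULN, and the clinical leads should confirm that they intend it.
3. **Remaining cases without an exit:** the clinical leads should state the action for persistent CK 3-5xULN with ALT/AST below 2xULN, and for persistent ALT/AST above 2xULN with CK below 3xULN. Moving the 5xULN rule across does not resolve either, and the choice is clinical.
4. **Tidy-up:** redirect ALT step (b2) to (c3) in both sections.

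The cost is a text-only amendment and a memo to sites. Items 1, 2 and 4 add no test or visit beyond what 6.2.3 and Appendix 6 already require. Item 3 may add a retest, depending on what the clinical leads decide.
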